3.4.2 Additional Effectiveness Endpoints

The following endpoints will be descriptively analyzed in Treatment Subjects at the indicated time points:

² Post-blanking CTI-dependent AFL or re-ablation or cardioversion for CTI-dependent AFL does not constitute Treatment Failure.

- **Persistent AF Acute Procedural Success**
Defined in **Section 3.3.1** at the conclusion of the Index Procedure / Rescheduled Index Procedure
- **Persistent AF Chronic Success**
Defined in **Section 3.3.2** through the Day 360 assessment
- **Single Procedure Treatment Success**
Treatment Success as defined in **Section 3.3.1** but counting subjects with any re-ablation for AT, AFL, or AT as Treatment Failures
- **Off Drug Treatment Success**
Treatment Success as defined in **Section 3.3.1** but counting subjects treated with any Class I / III AAD after Day 90 as Treatment Failures
- **Re-Ablation Rate**
Defined as the proportion of subjects who receive one or more re-ablations during study follow-up for AF, AFL, or AT, at any time during follow-up, and subdivided by re-ablation during Days 0 – 90 and by Days 91 and thereafter.

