7.13.2 Other Re-Ablation Procedures

For a second re-ablation during the Blanking Period and for any re-ablation after the Blanking Period, any commercially available ablation catheter may be used for re-ablation.

The FARAPULSE Pulsed Field Ablation System is not permitted to be used for these procedures.

Such re-ablations constitute Treatment Failures, and therefore during such procedures other sites may be ablated at Investigator discretion.

The following data will be collected for these procedures:

- Adverse events
- During re-ablation procedures, a mapping procedure will be performed to characterize the reconnection status for each originally treated PV and the PW (if a left-sided re-ablation), and the CTI, to characterize lesion durability.
- Limited ablation data

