COVID-19 Related Disruptions	A disruption to any study procedure resulting directly or indirectly from the COVID 19 pandemic, including but not limited to subject illness, study site restrictions and limitations, shipping / manufacturing interruptions, significant changes in regulatory guidance and / or governmental restrictions on travel, association, and the prioritization of healthcare resources.
Dates	
 • Consent Date: The date a subject signs the ICF. • Exit Date: The date on which a subject's study participation ends. • Onset Date: The date on which a condition or AE begins. • Start Date: Day 0, the date of the Index Procedure or Rescheduled Index Procedure
Day (or Study Day)	A Day is an enumerated day of follow-up that begins on an Enrolled Subject's Start Date (Day 0).
Detectable AF, AFL, or AT	
Detectable AF, AFL or AT is an episode of AF, AFL or AT which:
 
 • Is permanently recorded for review on a study-specific ECG, EM or Holter monitor 
 ○ Excludes arrhythmias recorded on other devices including implantable monitors and consumer wearables not specified in the ADVANTAGE AF Study procedures. • Contains at least 30 seconds of continuous interpretable signal 
 ○ Exception: Continuous AF, AFL or AT for the entirety of a 12 lead ECG constitutes Detectable AF, AFL or AT if the continuous interpretable signal is 10 seconds or longer • Includes symptomatic and asymptomatic episodes. • Excludes CTI isthmus-dependent AFL
Failed AAD	
Failed AADs include any and all Class I / III AAD determined at the time of enrollment to have been failed for effectiveness or intolerance. Failed AADs do not include Class I / III AADs determined at the time of enrollment solely to be contraindicated.
 
Failed AADs must be established as part of the Baseline Assessment for agent, type of failure (arrhythmia recurrence or AAD intolerance) and the maximum failed dose (the total daily dose at which such failure occurred).

Intent Subjects	Intent Subjects are defined in Section 6.6.3.
Non-Failed AAD	
A Non-Failed AAD is:
 
 • Any Class I / III AAD not established at the Baseline Assessment as a Failed AAD • Any Failed AAD used after Day 90 at a daily dose exceeding the maximum failed dose established at the Baseline Assessment

Term	Definition

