	
 • Death • Cardiac tamponade / perforation • Pericarditis • Any PFA system related or PFA procedure-related cardiovascular or pulmonary adverse event 	Day 0 – Day 30
The CSAE components of the PSE are defined in Table 3.3-2 .		
ADDITIONAL SAFETY ENDPOINTS	
 • Primary Safety Endpoint Through Day 360 Assessment • Composite Non-Serious Adverse Event • Related AEs • Any SAE • Post-Blanking Arrhythmia Hospitalizations • Post-Blanking Cardioversions • Coronary Spasm Events • Adverse Effects of Intraprocedural Administration of Nitroglycerin 	

A Prospective Single Arm Open Label Study of the FARAPULSE Pulsed Field Ablation System in Subjects with Persistent Atrial Fibrillation
 
The ADVANTAGE AF Study – Phase 2
	
PRIMARY EFFECTIVENESS ENDPOINT	
The primary effectiveness endpoint (PEE) is the proportion of LUX-Dx monitored Treatment Subjects with Treatment Success through the Day 360 Assessment.
 
Treatment Success is defined as:
 
 1. Persistent AF Acute Procedural Success AND 2. Persistent AF Chronic Success, defined as freedom from the following after the Blanking Period (excluding documented CTI-dependent flutter if subject was not treated with the FARAPPOINT PFA Catheter): 
 i. Arrhythmia: Occurrence of any Detectable AF, AFL or AT ii. Re-ablation: Any re-ablation for AF, AFL or AT iii. Cardioversion: Any electrical cardioversion for AF, AFL or AT iv. AAD Use: Use of a Non-Failed Class I / III AAD or amiodarone.
ADDITIONAL EFFECTIVENESS ENDPOINTS	
 • CTI-Mediated AFL Treatment Success • Re-Ablation Rate for CTI-Mediated AFL • Persistent AF Acute Procedural Success • Persistent AF Chronic Success • Freedom from Detectable AF, AFL, AT • Freedom from Symptomatic Recurrence and Intervention to Treat AF, AFL, or AT • Single Procedure Treatment Success • Off Drug Treatment Success • Re-Ablation Rate • AF, AFL, and AT Burden • Healthcare Utilization by AF, AFL, and AT Burden • Healthcare Utilization by AF, AFL, or AT Recurrence Duration
PROCEDURAL ASSESSMENTS	
Assessments of procedure durations
 
 • Procedure Time • LA Dwell Time • PVI and PWI Ablation Time • CTI Ablation Time • Fluoroscopy Time 
Characterization of lesion sets
 
 • PVI Ablations • PWI Ablations • CTI Ablations • Other Ablations

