3.4.2 Persistent AF Chronic Success

Persistent AF Chronic Success is defined as freedom from any of the following through the Day 360 Assessment after the Blanking Period, excluding documented CTI-dependent AFL¹:

- a. **Arrhythmia:** Occurrence of any Detectable AF, AFL or AT
- b. **Re-ablation:** Any re-ablation for AF, AFL or AT
- c. **Cardioversion:** Any electrical cardioversion for AF, AFL or AT
- d. **AAD Use:** Use of a Non-Failed Class I / III AAD or amiodarone

Within the Blanking Period, recurrent arrhythmias can be managed with AADs, cardioversion or one re-ablation procedure with the FARAPULSE PFA System without constituting Persistent AF Chronic Failure. Titration of Class I/III antiarrhythmic medications are allowed during the Blanking Period. Subjects are allowed to remain on Class I/III antiarrhythmic medications at the historic maximum ineffective dose (prior to the ablation procedure) after the 90-day Blanking Period, except amiodarone. Subjects that undergo more than one re-ablation procedure within the Blanking Period will be classified as a Persistent AF Chronic Failure. Complete definitions of the endpoint terms (including Blanking Period, Detectable AF, AFL, or AT, Failed AAD and Non-Failed AAD), can be found in **Section 23.2**.

¹ Post-blanking CTI-dependent AFL or re-ablation or cardioversion for CTI-dependent AFL does not constitute Treatment Failure if the subject did not have a CTI ablation with the FARAPULSE PFA Catheter but will be a Treatment Failure if the subject did receive ablation with the FARAPULSE PFA Catheter.

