8.1.2 Primary Effectiveness Endpoint

The Primary Effectiveness Endpoint (PEE) is defined in **Section 3.4**. The definition of the PEE remains consistent with the ADVANTAGE AF Phase 1 PEE, apart from the definition of Detectable AF, AFL, or AT (Section 23.2), which has been adjusted for recurrence monitoring using an ICM in place of standard recurrence monitoring methods.

The observed one-year treatment success based on standard non-continuous monitoring methods (12-lead ECG at each follow-up visit, 24-hour Holter every 6 months, regular or scheduled event monitor transmissions, and symptom-driven event monitoring) is expected to be higher than what could be observed from an ICM, given its capability of continuously monitoring the heart rhythm during the entire period of observation. Based on a comparison with data obtained from the CIRCA-DOSE trial which included subjects with paroxysmal AF, it has been estimated that an arrhythmia recurrence assessment based on ECG, Holter monitoring and symptomatic episodes captured from event monitors would lead only to 40.9% sensitivity and 65.3% negative predictive value when compared to an ICM¹⁹.

While the value in implementing continuous arrhythmia monitoring post AF ablation is well accepted, to date no standards are defined for determining one-year treatment success when using ICMs for arrhythmia monitoring, leading to inconsistency in methodology including but not limited to, different episode duration cutoffs, variable ICM programming, and inconsistency in symptom-driven monitoring. The limited number of studies assessing post ablation outcomes with ICM to date report variable one-year arrhythmia recurrence rates ranging from 27% to 64%²²⁻³². These studies use different arrhythmia duration criteria (from >30 seconds to 24 hours), different timelines for ICM insertion in respect to ablation procedure, and different endpoint definitions (recurrence vs burden). Accordingly, results obtained from different ablation studies using ICM are heterogeneous and not comparable, so they cannot be analyzed collectively to form a hypothesis for the ADVANTAGE Phase 2 PEE based on continuous monitoring.

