8.3.6 Treatment Success Rate by Arrhythmia Detection Method

PersAF Treatment Success rates through Day 360 Assessment will be compared between ADVANTAGE AF Phase 1 and Phase 2 Treatment Subjects to assess differences in chronic success when using the continuous monitoring from an ICM to simulate non-continuous monitoring for recurrence compared to standard assessment based on true Holter monitoring and periodic

transmissions from event monitors. A propensity score analysis utilizing inverse probability of treatment weights (IPTW) will be used to estimate the absolute difference in PersAF Treatment Success rates between detection groups (ICM vs. Standard) while minimizing the effects of confounding variables. Details of this analysis will be included in the Appendix A of the ADVANTAGE AF SAP.

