Detectable AF, AFL, or AT	
Detectable AF, AFL or AT is an episode of AF, AFL or AT which:
 
 • Is recorded for review on a LUX-Dx ICM and meets any of the following criteria: 
 ○ Adjudicated symptomatic (patient initiated) recording that contains ≥ 30 seconds of continuous atrial arrhythmia. ○ Adjudicated AF or AT episode captured by LUX-Dx that contains at least 30 seconds of atrial arrhythmia and overlaps a simulated bi-monthly, 2 minute event monitor transmission period. ○ Adjudicated AF or AT episode captured by LUX-Dx that contains at least 30 seconds of atrial arrhythmia and overlaps a simulated 24 hour holter period occurring the day before the Day 180 and Day 360 Assessments (or last day of respective visit window if visit(s) is missed)⁸. • Continuous AF, AFL or AT for the entirety of a 12 lead ECG if the continuous interpretable signal is 10 seconds or longer • Exclusions: 
 ○ CTI isthmus-dependent AFL if the subject did not have a CTI ablation with the FARAPoint PFA Catheter ○ Arrhythmias recorded on other devices, including implantable monitors and consumer wearables, not specified in the ADVANTAGE AF Study procedures
Failed AAD	
Failed AADs include any and all Class I / III AAD determined at the time of enrollment to have been failed for effectiveness or intolerance. Failed AADs do not include Class I / III AADs determined at the time of enrollment solely to be contraindicated.
 
Failed AADs must be established as part of the Baseline Assessment for agent, type of failure (arrhythmia recurrence or AAD intolerance) and the maximum failed dose (the total daily dose at which such failure occurred).

Intent Subjects	
Intent Subjects are defined in Section 6.6.3 of the ADVANTAGE Phase 1 Protocol.

Non-Failed AAD	
A Non-Failed AAD is:
 
 • Any Class I / III AAD not established at the Baseline Assessment as a Failed AAD • Any Failed AAD used after Day 90 at a daily dose exceeding the maximum failed dose established at the Baseline Assessment

⁸ Day prior to the Day 180 and Day 360 visits was selected to prevent overlap in the rhythm captured by the visit-required 12-lead ECG.

Term	Definition
Persistent atrial fibrillation	PersAF is defined as continuous AF that is sustained beyond 7 days, but not greater than 12 months duration.

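### The cross-phase comparison in Appendix A 8.3.6 reads the Phase 1 versus Phase 2 difference as a monitoring effect, but the two phases score CTI-dependent flutter differently

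*Combined protocol and SAP*

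**What the plan says.** **The comparison.** Appendix A 8.3.6 says "PersAF Treatment Success rates through Day 360 Assessment will be compared between ADVANTAGE AF Phase 1 and Phase 2 Treatment Subjects". It estimates the absolute difference with inverse probability of treatment weights and names the two groups by detection method, ICM or standard. Details are left to Appendix A of the SAP. Appendix A 4.1.1 keeps Phase 1 subjects on the protocol version under which they enrolled.

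**Phase 1 rule.** The footnote to 3.3.2 reads: "Post-blanking CTI-dependent AFL or re-ablation or cardioversion for CTI-dependent AFL does not constitute Treatment Failure". The Phase 1 definition of Detectable AF, AFL or AT (23.2) carries the same unconditional exclusion: "Excludes CTI isthmus-dependent AFL".

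**Phase 2 rule.** The exclusion is conditional. The Appendix A synopsis has "excluding documented CTI-dependent flutter if subject was not treated with the FARAPPOINT PFA Catheter", and Appendix A 23.2 excludes "CTI isthmus-dependent AFL if the subject did not have a CTI ablation with the FARAPoint PFA Catheter". Footnote 1 to Appendix A 3.4.2 adds that such flutter, or re-ablation or cardioversion for it, "will be a Treatment Failure if the subject did receive ablation with the FARAPULSE PFA Catheter". Appendix A 4.1.2 expects about 30% of Treatment Subjects, an estimated 80, to receive FARAPOINT.

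**How the change is explained.** Appendix A 8.1.2 says the primary effectiveness endpoint matches Phase 1 except for the Detectable AF, AFL or AT definition, "which has been adjusted for recurrence monitoring using an ICM in place of standard recurrence monitoring methods".

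**Re-ablation wording.** Phase 1 7.13.2 and Appendix A 7.14.2 both say of any post-blanking re-ablation: "Such re-ablations constitute Treatment Failures, and therefore during such procedures other sites may be ablated at Investigator discretion". Neither makes an exception for CTI flutter.

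**The concern.** The purpose of 8.3.6 is to show what simulated intermittent monitoring from an ICM does to the success rate, compared with real Holter and event monitors. That reading needs the same event to be scored the same way in both phases. Here, the same documented flutter is scored as success in a Phase 1 subject, even after RF ablation of the CTI, and as failure in a FARAPOINT-treated Phase 2 subject. Under the endpoint definitions this can only lower Phase 2 success, so part of any Phase 2 deficit would be credited to monitoring.

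A reader of 8.1.2 would not find this out there. That section gives ICM monitoring as the only reason for the changed definition. It does not mention that the re-ablation and cardioversion components changed too, and those lie outside the Detectable AF, AFL or AT definition.

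What is at stake is the interpretation of a supportive analysis. The test against the 40% goal, the safety endpoint and study success do not depend on it.

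**Working it through.** Section 8.3.6 states no sample size, power or expected difference, so there is no figure to reproduce. The check sets the rules side by side and then illustrates the size.

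**1. The rules side by side (endpoint definitions)**

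| Post-blanking event | Phase 1, any subject | Phase 2, no FARAPOINT CTI ablation | Phase 2, FARAPOINT CTI ablation |
|---|---|---|---|
| Documented CTI-dependent flutter | not a failure | not a failure | failure |
| Re-ablation or cardioversion for it | not a failure | not a failure | failure |

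Take identical patients, rhythms and detection, with covariates perfectly balanced. The last column still differs from the first. Weighting acts on covariates, so it leaves this difference in place. None of the seven sensitivity analyses in Appendix A 8.3.3 varies this rule.

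**2. Share affected**

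From Appendix A 4.1.2, f = 80/258 = 0.310.

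**3. Size of the shift in Phase 2 success**

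The documents give no rate of CTI-flutter recurrence after FARAPOINT. The rates below are assumptions.

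(a) If a share x of FARAPOINT subjects fails by CTI flutter alone, shift = f × x:
- x = 2%: 0.62 points
- x = 5%: 1.55 points
- x = 10%: 3.10 points

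(b) If r is a recurrence rate independent of other failures, and success is otherwise 55% (the expected rate in Appendix A 8.1.2.2), shift = r × 0.55 × f:
- r = 2%: 0.34 points
- r = 5%: 0.85 points
- r = 10%: 1.71 points
- r = 3/17 = 17.6%: 3.01 points
- r = 20%: 3.41 points

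The 20% is the complement of the low end of the 80–100% long-term success quoted for RF in Appendix A 1.1, a different energy source. The 3/17 is the loss of bidirectional block at remapping in Appendix A 1.2 (14 of 17 retained); it measures durability of block, not clinical recurrence.

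Replacing 55% by the 40% goal or the 67.23% meta-analytic rate (Phase 1 8.1.2) gives 1.24 or 2.08 points at r = 10%, and 2.48 or 4.17 points at r = 20%.

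**4. Scale against sampling error**

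The unweighted SE of the phase difference at 55% is √(2 × 0.55 × 0.45 / n):
- n = 258 per phase: 4.38 points
- n = 232 per phase (258 less 10% attrition): 4.62 points

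Coverage of a nominal 95% interval for the monitoring effect is Φ(1.96 − d) − Φ(−1.96 − d), where d = shift/SE:
- shift 1.71: d = 0.37 to 0.39, coverage about 93%
- shift 3.41: d = 0.74 to 0.78, coverage about 88 to 89%

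**5. Consistency within each phase**

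The re-ablation sentence in Phase 1 7.13.2 conflicts with the Phase 1 footnote. The identical sentence in Appendix A 7.14.2 conflicts with footnote 1 for subjects without FARAPOINT. If 7.13.2 governed Phase 1, re-ablation for CTI flutter would count as failure there, and the direction of the shift would no longer be certain.

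Footnote 1 also names a FARAPULSE catheter where the synopsis and 23.2 name FARAPOINT, and its last clause omits the CTI. Every Treatment Subject receives at least one pulsed field application (Phase 1 6.6.5), so a literal reading could reach all of them.

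**The case against.** The strongest reply is that 8.3.6 is a summary paragraph. It defers details to a SAP appendix, which is the natural place for an outcome derivation. What is shown is that the protocol states no common rule, not that the analysis will lack one. That stands as a limit on the finding.

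The size is also modest, and scenario (b) is an upper-end illustration. An asymptomatic LUX-Dx episode counts only if it overlaps a sampled two-minute window or a simulated Holter day, and AT detection is set at four hours at 110 bpm, so not every recurrence would be scored. Weighting would ordinarily widen the SE and make the relative bias smaller. This also stands. However, the bias is systematic and falls on the one quantity that 8.3.6 estimates.

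A common rule will not give a clean monitoring contrast. The CTI catheter, eligibility after prior CTI ablation and geography still differ between phases. BeatLogic separates only atrial from non-atrial arrhythmia, so an episode whose CTI dependence is never confirmed on a 12-lead ECG would still be scored as failure. These points limit what the fix achieves but do not argue against it.

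Finally, the conditional rule is printed in 23.2 and footnote 1, and the catheter name looks like a slip: Appendix A 7.7.2.5 bars FARAWAVE from CTI lesions, so the footnote's reference to CTI ablation can only mean FARAPOINT. True, but 8.1.2 still gives an incomplete account of the change, and the re-ablation conflict decides who is a failure.

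**Conclusion.** The concern holds. As the protocol is written, 8.3.6 mixes a difference in outcome definition into a contrast labelled as detection method, and weighting cannot take it out. Under the endpoint definitions the effect is to lower Phase 2 success. The illustrated shifts run from 0.3 to 3.4 points in the independent-recurrence scenario at 55% success, and from 0.6 to 3.1 points if 2% to 10% of FARAPOINT subjects fail by CTI flutter alone. All are below one SE.

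This rests on 80 of 258 subjects receiving FARAPOINT, on assumed recurrence rates, on the footnotes governing rather than 7.13.2 and 7.14.2, and on the SAP appendix not already setting a common rule. The deliberate Phase 2 endpoint rule is not criticised, and nothing here bears on the primary tests, study success or the covariate analyses in 8.3.4 and 8.3.7. It is a change that should be made, with medium confidence.

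**What to change.** 1. In 8.3.6, or in Appendix A of the SAP, derive Treatment Success in both phases under one rule: documented CTI-dependent flutter, and re-ablation or cardioversion for it, excluded for all subjects. Show the protocol-rule result beside it.
2. State that this removes only the documented CTI-flutter component, and list the phase differences that remain: CTI catheter, prior-CTI-ablation eligibility and geography.
3. In 8.1.2, add that the CTI-flutter exclusion is now conditional and that the handling of re-ablation and cardioversion for CTI flutter changed as well.
4. Reconcile Phase 1 7.13.2 with the footnote to Phase 1 3.3.2, and Appendix A 7.14.2 with footnote 1 to Appendix A 3.4.2, on whether post-blanking re-ablation for CTI flutter is a Treatment Failure. Do this before the 8.3.6 derivation is fixed.
5. Reconcile the catheter named in footnote 1 with the synopsis and Appendix A 23.2.

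The cost is one derived variable, one extra result row, one sentence and wording corrections. The Phase 1 derivation is the existing one under its footnote. For Phase 2, Appendix A 3.5.2 already requires 12-lead ECG confirmation of CTI-mediated flutter and separates CTI-only re-ablation. The reason for a cardioversion is already needed to apply the exclusion in Phase 1 and in Phase 2 subjects without FARAPOINT. The primary endpoint and its test stay as they are.

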8.3.7 Multivariable Analyses

For the Primary Safety Endpoint and Primary Effectiveness Endpoint, univariable analyses of the following covariates will be performed, and any found to be significantly associated with the outcome at the 0.15 alpha level will be included as covariates in a multivariable regression model. Backward selection with 0.15 alpha level stay criterion will be used to determine the final multivariable model.

The list of baseline covariates includes, but is not necessarily limited to:

- Subject demographics (e.g., age, gender)
- Subject baseline characteristics (e.g., LVEF, cardioversion history, BMI, LA diameter, and years since AF diagnosis)
- Index Procedure lesion sets
 - PVI + LAPW ablation alone versus PVI + LAPW plus additional ablations
 - CTI ablation versus no CTI ablation
- Operator learning curve (e.g., number of prior procedures completed by operator at time of procedure, counting at a minimum, the procedures from ADVANTAGE AF Phase 1 and Phase 2)
- Mapping of the PW during Index Procedure

Additional covariates for the Primary Effectiveness Endpoint only include:

- Amiodarone use post Index Procedure versus no Amiodarone use post Index Procedure
- LUX-Dx model (LUX-Dx II+ [M312] vs LUX-Dx [M301] or LUX-Dx II [M302])

